5.5.3. Lenalidomide Drug Dispensing Requirements (applies to ex-US sites only)

In investigational studies, lenalidomide will be dispensed through a qualified healthcare professional (including but not limited to, nurses, pharmacists and physicians) and lenalidomide prescribers must be included on the Form FDA 1572. These healthcare professionals will be trained by Celgene or designee in requirements specific to counseling of subjects. Each site is

required to have two trained counselors at all times. Once trained, these healthcare staff will counsel the subjects prior to medication being dispensed to ensure that the subject has complied with all requirements including use of birth control and pregnancy testing (FCBP) and that the subject understands the risks associated with lenalidomide. This step will be documented with a completed Education and Counseling Guidance Document ([Appendix 8](#)), and no drug will be dispensed until this step occurs. Counseling includes verification with the subject that required pregnancy testing was preformed and results were negative. A Lenalidomide Information Sheet ([Appendix 8](#)) will be supplied with each medication dispense.

Pregnancy Testing

Pregnancy tests for females of childbearing potential. A female of childbearing potential (FCBP) is a sexually mature female who: 1) has not undergone a hysterectomy or bilateral oophorectomy; or 2) has not been naturally postmenopausal (amenorrhea following cancer therapy does not rule out childbearing potential) for at least 24 consecutive months (ie, has had menses at any time in the preceding 24 consecutive months).

Pregnancy tests must occur within 10–14 days and again within 24 hours prior to initiation of Cycle 1 of lenalidomide. FCBP with regular or no menstruation must have a pregnancy test weekly for the first 28 days and then every 28 days while on lenalidomide therapy (including breaks in therapy); at discontinuation of lenalidomide and at Day 28 post the last dose of lenalidomide. A FCBP with irregular menstruation must have a pregnancy test weekly for the first 28 days and then every 14 days while on lenalidomide therapy (including breaks in therapy), at discontinuation of lenalidomide and at Day 14 and Day 28 post the last dose of lenalidomide (see [Appendix 8](#)).

Counseling

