7.5.5.3. Pregnancy Test

A pregnancy test (urine or serum) with a sensitivity of 25 mIU/mL must be done in accordance with Celgene Corporation's Revlimid REMS™ or global Pregnancy Prevention Program (PPP) guidelines for females of childbearing potential (FCBP) only. If the pregnancy test is positive at Screening, the subject is not eligible.

A FCBP is a sexually mature female who: 1) has not undergone a hysterectomy or bilateral oophorectomy; or 2) has not been naturally postmenopausal (amenorrhea following cancer therapy does not rule out childbearing potential) for at least 24 consecutive months (ie, has had menses at any time in the preceding 24 consecutive months).

Pregnancy tests must occur within 10–14 days and again within 24 hours prior to initiation of Cycle 1 of lenalidomide. A FCBP with regular or no menstruation must have a pregnancy test weekly for the first 28 days and then every 28 days while on lenalidomide therapy (including breaks in therapy); at discontinuation of lenalidomide and at Day 28 post the last dose of lenalidomide. A FCBP with irregular menstruation must have a pregnancy test weekly for the first 28 days and then every 14 days while on lenalidomide therapy (including breaks in therapy), at discontinuation of lenalidomide and at Day 14 and Day 28 following lenalidomide discontinuation.

In order to allow for drug delivery in the US, pregnancy testing can be performed on Days 22-28 of each cycle. A pregnancy test may be performed more frequently if required by local and national requirements.

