8.3. Treatment Phase

Subjects must continue to meet eligibility criteria pre-dose on Day 1 Cycle 1 in order to enroll into the study. Safety laboratory assessments performed within 48 hours prior to Day 1 of any cycle of study drug may be used for dosing.

8.3.1. Cycle 1, Day 1

Pre-dose

- Complete physical exam including weight
- ECOG performance status
- Vitals signs including blood pressure, heart rate, respiratory rate, and body temperature
- Collect blood samples for the following laboratory tests:
 - Hematology
 - Serum chemistry
 - T/B/NK
 - Biomarkers
 - Serum immunoglobulins (**Phase 2 only**)
- Calculate creatinine clearance
- Review of AEs and concomitant medications
- Obtain urine or serum pregnancy test for women of childbearing potential within 24 hours prior to initiation of Cycle 1 of lenalidomide according to [Section 7.5.5.3](#).
- Review inclusion and exclusion criteria to confirm subject eligibility prior to dosing
- Lenalidomide counseling

Dosing and Postdose

- Dispense ibrutinib and lenalidomide
- Review study drug compliance instructions
- Administration of ibrutinib, lenalidomide and rituximab
- Review of AEs and concomitant medications

8.3.2. Cycle 1, Day 8

Predose

- Symptom directed physical exam including weight
- ECOG performance status
- Vitals signs (including blood pressure, heart rate, respiratory rate, and body temperature)
- Collect blood samples for the following laboratory tests:
 - Hematology
 - Serum chemistry
- Review study drug compliance
- Review of AEs and concomitant medications

- Obtain urine or serum pregnancy test for women of childbearing potential according to [Section 7.5.5.3](#).

Dosing and Postdose

- Administration of ibrutinib and lenalidomide

8.3.3. Cycle 1, Day 15

Predose

- Symptom directed physical exam including weight
- ECOG performance status
- Vitals signs (including blood pressure, heart rate, respiratory rate, and body temperature)
- Collect blood samples for the following laboratory tests:
 - Hematology
 - Serum chemistry
- Review study drug compliance
- Review of AEs and concomitant medications
- Obtain urine or serum pregnancy test for women of childbearing potential according to [Section 7.5.5.3](#).

Dosing and Postdose

- Administration of ibrutinib and lenalidomide

8.3.4. Cycle 1, Day 22

Predose

- Symptom directed physical exam including weight
- ECOG performance status
- Vitals signs (including blood pressure, heart rate, respiratory rate, and body temperature)

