8.3.5. Cycle 2, Day 1**Predose**

- Complete physical exam including weight
- ECOG performance status
- Vitals signs (including blood pressure, heart rate, respiratory rate, and body temperature)
- Collect blood samples for the following laboratory tests:
 - Hematology
 - Serum chemistry
 - T/B/NK
 - Biomarkers
- Collect pre-dose PK sample (**Phase 2 only**)
- Obtain urine or serum pregnancy test for women of childbearing potential according to [Section 7.5.5.3](#)
 - FCBP with regular or no menstruation must have a pregnancy test weekly for the first 28 days and then every 28 days while on lenalidomide therapy (including breaks in therapy).
 - FCBP with irregular menstruation must have a pregnancy test weekly for the first 28 days and then every 14 days while on lenalidomide therapy (including breaks in therapy).
- Calculate creatinine clearance
- Review study drug compliance
- Review of AEs and concomitant medications
- Lenalidomide counseling

Dosing and Postdose

- Administration of ibrutinib, lenalidomide and rituximab
- Collect PK samples (**Phase 2 only**) at 1 hour (\pm 15 minutes), 2 hours (\pm 15 minutes), 4 hours (\pm 30 minutes), and 6 hours (\pm 1 hour) post-dose

8.3.6. Cycle 2, Day 15

Predose

- Symptom directed physical exam including weight
- ECOG performance status
- Vitals signs (including blood pressure, heart rate, respiratory rate, and body temperature)
- Collect a blood sample for the following laboratory test:
 - Hematology
 - Serum Chemistry
- Review study drug compliance
- Review of AEs and concomitant medications
- Females with irregular menstruation must have a pregnancy test every 14 days while on lenalidomide therapy (including breaks in therapy).

Dosing and Postdose

- Administration of ibrutinib and lenalidomide.

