Pregnancy Test (serum or urine) ^j		X	X	X	X	X	X ^j	X	X ^j	X	X	X	X	X ^j
T/B/NK Cell Count ^k		X			X	X		X		X	X ^k	X ^k	X ^k	X
Serum Immunoglobulins (Ig ^l) (Phase 2)						X					X ^l	X ^l	X ^l	X
Biomarker Blood Sample ^k		X				X	X	X		X	X ^k	X ^k	X ^k	X
PK Blood Sampling ^m (Phase 2)						X ^m	X ^m							
Radiologic Tumor Assessment														
CT Neck, Chest, Abdomen, Pelvis ⁿ		X						X		X	X ^{n,o}		X	
PET or PET/CT ⁿ		X									X ^{n,o}		X	
Other														
Survival Status ^p														X ^p
Subsequent Anticancer Therapy														X ^p

Abbreviations: C=cycle; CT=computed tomography; D=day; ECG=electrocardiogram; ECOG=Eastern Cooperative Oncology Group; EOT=End-of-Treatment Visit; LTFU=Long-Term Follow Up; RE=Response Evaluation; PD=progressive disease; PET=positron emission tomography; PO=oral; RFU=Response Follow Up

Footnotes for PCYC-1123-CA Schedule of Assessments:

^a CT/MRI and PET scans may be done per the Investigator's discretion during the response follow-up period.

^b Study Drug diary must be provided to the subjects at the beginning of each Day 1 visit to record daily dosing. Site personnel must instruct the subjects to bring the completed diary card with any used and unused study drugs at each study visit. Site personnel must reconcile and document the returned capsules from the subjects at each visit to ensure compliance.

^c **Phase 2 only:** A fresh tissue sample, archived unstained slides or an archived paraffin block must be sent to central lab for determination of DLBCL subtype by GEP and IHC using the Hans method **at Screening to confirm eligibility for enrollment.** For subjects in **Phase 1b**, available tissue (archived or fresh) will be sent to central lab at Screening for DLBCL subtyping. (Local laboratory results for DLBCL subtype for subjects in the Phase 1b may be collected). The tumor sample(s) can be archival tissue from original diagnosis, from relapsed or refractory disease, or a fresh (recent) biopsy, if done to confirm eligibility for this study.

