^j Must be done in accordance with Celgene Revlimid REMTM program (US Sites) or global Pregnancy Prevention Program (PPP) guidelines (Ex-US Sites) for females of childbearing potential (FCBP). Day 15 of each Cycle only applies if a subject's menstruation is irregular. Serum or urine depending on site standard method. If positive at Screening Visit, the subject is not eligible to enroll. See [Appendix 7](#) and [Appendix 8](#) for pregnancy testing frequency requirements.

^k T/B/NK cell count and biomarkers should be done at pre-dose on Day 1 of Cycles 1, 2, 3, at response evaluation (ie, Day 1 Cycles 4, 7, 10, 13, 16, 19, 22, 25, and then every 6 cycles thereafter) and EOT Visits.

^l **Phase 2 only:** Serum Ig will be taken pre-dose Day 1 Cycle 1. Samples will also be taken at all response evaluation visits (eg, Cycle 4, 7, 10, etc.) and EOT Visit.

^m **Phase 2 only:** PK samples will be drawn according to the schedule [Table 9](#). For subjects who must take strong or moderate CYP3A inhibitors while on treatment with ibrutinib, additional PK blood samples for evaluation of ibrutinib exposure is requested.

ⁿ Pretreatment tumor assessment should be performed within 28 days before the first dose. A CT scan (with contrast unless contraindicated) of the neck, chest, abdomen, and pelvis and any other disease sites and a PET or PET/CT scan are required for the pretreatment tumor assessment. Thereafter, a PET scan is to be performed to confirm CR if PET result was positive at Screening or may be performed at anytime if clinically indicated. During treatment, CT/MRI scans will be done for tumor assessments within 7 days prior to Day 1 of Cycle 4 and Cycle 7, then every 3 cycles up to Cycle 25, and then every 6 cycles thereafter, until PD or use of alternative anticancer therapy. In the event that CT contrast is contraindicated, MRI of the abdomen and pelvis with contrast and CT of the chest and neck may be performed as an alternative. Lesions in anatomical locations that are not well visualized by CT may be measured at baseline from MRI instead and should continue to be measured from MRI until disease progression. Follow the [Cheson 2007](#) (Phase 1b) [Appendix 5](#) and [Cheson 2014](#) (Phase 2) [Appendix 6](#).

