- FCBP with regular or no menstrual cycles must agree to have pregnancy tests weekly for the first 28 days of lenalidomide treatment, including dose interruptions and then every 28 days throughout the remaining duration of lenalidomide treatment, including dose interruptions, at lenalidomide discontinuation, and at Day 28 following lenalidomide discontinuation. If menstrual cycles are irregular, the pregnancy testing must occur weekly for the first 28 days of lenalidomide treatment, including dose interruptions, and then every 14 days throughout the remaining duration of lenalidomide treatment, including dose interruptions, at lenalidomide discontinuation, and at Day 14 and Day 28 following lenalidomide discontinuation.
- At each visit, the Investigator must confirm with the FCBP that she is continuing to use two reliable methods of birth control at each visit during the time that birth control is required.
- If pregnancy or a positive pregnancy test does occur in a study patient, lenalidomide must be immediately discontinued.
- Pregnancy testing and counseling must be performed if a patient misses her period or if her pregnancy test or her menstrual bleeding is abnormal. Lenalidomide treatment must be temporarily discontinued during this evaluation.
- Females must agree to abstain from breastfeeding during study participation and for at least 28 days after lenalidomide discontinuation.

Male Patients:

- Must practice complete abstinence or use a condom during sexual contact with pregnant females or females of childbearing potential throughout the entire duration of lenalidomide treatment, during dose interruptions and for at least 90 days following lenalidomide discontinuation, even if he has undergone a successful vasectomy.
- If pregnancy or a positive pregnancy test does occur in the partner of a male study patient during study participation, the Investigator must be notified immediately.
- Male patients should not donate semen or sperm during therapy or for at least 90 days following discontinuation of lenalidomide.

Additional Precautions

- Patients should be instructed never to give lenalidomide to another person.
- Patients should not donate blood during therapy and for at least 28 days following discontinuation of lenalidomide (90 days for male subjects).
- Only enough lenalidomide for one cycle of therapy may be prescribed with each cycle of therapy.

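### Appendix 1 footnote j limits the Day 15 pregnancy test to irregular menstruation in every cycle, which read literally drops a Cycle 1 test that the rest of the protocol requires

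*Protocol*

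**What the plan says.** The pregnancy-test row in the Appendix 1 schedule carries the superscript on its label, "Pregnancy Test (serum or urine) ^j", so footnote j governs the whole row. The footnote opens by requiring compliance with the REMS program (US) or the Pregnancy Prevention Program (ex-US). It then says "Day 15 of each Cycle only applies if a subject's menstruation is irregular", and it closes by sending the reader to Appendices 7 and 8 "for pregnancy testing frequency requirements".

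The other statements of the rule are:

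- Section 5.5.3 (ex-US dispensing): "FCBP with regular or no menstruation must have a pregnancy test weekly for the first 28 days and then every 28 days".
- Section 7.5.5.3: "A FCBP with regular or no menstruation must have a pregnancy test weekly for the first 28 days".
- Appendix 7 (US sites): "FCBP with regular or no menstrual cycles must agree to have pregnancy tests weekly for the first 28 days of lenalidomide treatment".
- Appendix 8 (ex-US sites), Sections 2.4 and 2.5.2.1, gives the same weekly rule for regular or absent cycles. The counselling form in its Section 3 gives it for regular cycles.
- Section 8.3.3 (Cycle 1 Day 15): "Obtain urine or serum pregnancy test for women of childbearing potential according to" Section 7.5.5.3, with no menstrual condition. Cycle 1 Days 8 and 22 have the same entry.
- Section 8.3.6 (Cycle 2 Day 15), where the restriction first appears in the visit procedures: "Females with irregular menstruation must have a pregnancy test every 14 days while on lenalidomide therapy".

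**The concern.** The footnote's Day 15 restriction has no exception for Cycle 1, yet Cycle 1 is the one cycle in which every woman of childbearing potential is meant to be tested weekly. The footnote therefore contradicts the body text and the two appendices that it cites.

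This matters because the schedule table is what sites commonly work from, and Section 7.7 sends them to Appendix 1 for when and how often samples are taken. Section 1.9 notes that lenalidomide carries a black box warning for embryo-fetal toxicity. A site that follows the sentence would omit one of the weekly tests in the first cycle and commit a protocol deviation while believing it was compliant. A site that does the test breaches nothing.

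**Working it through.** The plan states no figure to reproduce. The check compares the texts and counts days and doses.

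**Inputs**

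- Lenalidomide is dosed on Days 1-21 of a 28-day cycle (Section 5.5.4).
- Cycle 1 visits fall on Days 1, 8, 15 and 22 (Sections 8.3.1 to 8.3.4). Cycle 2 Day 1 is Study Day 29 (Section 5.1).
- Assumption: each test is done before dosing on the visit day. The Predose heading in Section 8.3.3 supports this for Day 15.

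**Step 1. Which cycles carry the restriction?**

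| Source | Cycle 1 Day 15, regular or no menstruation | Day 15 from Cycle 2, regular or no menstruation |
|---|---|---|
| Sections 5.5.3 and 7.5.5.3 | required (weekly) | not required (28-day interval) |
| Appendices 7 and 8 | required (weekly) | not required (28-day interval) |
| Visit procedures | required (8.3.3) | not required (8.3.6, 8.3.9) |
| Footnote j, Day 15 sentence alone | **not required** | not required |

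The sources agree from Cycle 2 onward. They differ only at Cycle 1 Day 15, where the footnote sentence stands alone.

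**Step 2. Intervals between tests for a woman with regular or no menstruation**

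- Weekly rule, tests on Days 1, 8, 15, 22, 29: 8 − 1 = 7, 15 − 8 = 7, 22 − 15 = 7, 29 − 22 = 7. The longest is 7 days.
- Footnote read literally, tests on Days 1, 8, 22, 29: 8 − 1 = 7, 22 − 8 = 14, 29 − 22 = 7. The longest is 14 days.

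**Step 3. Scheduled lenalidomide doses between consecutive tests**

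- Weekly rule: Days 1-7 give 7, Days 8-14 give 7, Days 15-21 give 7, Days 22-28 give 0. The most is 7.
- Footnote read literally: Days 1-7 give 7, Days 8-21 give 21 − 8 + 1 = 14, Days 22-28 give 0. The most is 14.

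On the literal reading the test after Day 8 falls on Day 22, after the last scheduled dose of the cycle. Dispensing would not prompt an earlier check, because Section 5.5.1 provides one cycle's supply at a time.

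**Step 4. After the correction**

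If the restriction begins at Cycle 2, the Cycle 1 tests fall on Days 1, 8, 15 and 22, as the weekly rule requires.

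**The case against.** The strongest reply is that the footnote corrects itself. It begins by requiring REMS or PPP compliance and ends by naming Appendices 7 and 8 as the source for frequency, and both give the weekly rule. The procedure for the very visit in question lists the test without condition. A missed test therefore needs a site to act on one sentence and disregard the rest of the footnote, Section 8.3.3, Section 7.5.5.3 and the risk-management program. Nothing in the documents shows that any site did so.

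The schedule grid also helps this side. Its extraction is damaged, so cells cannot be matched to visits with confidence. But whether the first cell of the row is Screening or Cycle 1 Day 1, Cycle 1 Day 15 would be the fourth or third cell, and both carry a plain X without the superscript.

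Finally, the correction may come too late to change practice. SAP Section 6, in a document dated 20APR2020, places the analysis due about 12 months after the last subject started treatment (or once all had stopped) close to a 2019 meeting. Cycle 1 was therefore probably over for everyone.

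Most of this stands as a limit on practical weight. It does not make the sentence right. A pointer to appendices that state a different rule leaves the footnote inconsistent with itself, and Section 7.7 sends sites back to Appendix 1. If Cycle 1 is finished, the correction still settles how an omitted Day 15 test should be classified.

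**Conclusion.** The point holds as a minor drafting error: the Day 15 restriction in footnote j is one cycle too broad. On the literal reading, a woman with regular or no menstruation loses one Cycle 1 test, the longest interval rises from 7 to 14 days, and the doses between tests rise from 7 to 14. These counts assume predose testing on the visit day and dosing as scheduled.

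The two negative tests before the first dose, the contraception rules and the Day 8 and Day 22 tests are untouched. The documents do not give the number of women of childbearing potential, so the number affected cannot be stated. Endpoints, sample size and the statistical analysis are unaffected.

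**What to change.** Replace the Day 15 sentence in footnote j with: *From Cycle 2 onward, the Day 15 test is needed only when menstruation is irregular; in Cycle 1 the Day 15 test is required for all FCBP.* Leave Sections 5.5.3, 7.5.5.3, 8.3.3 and 8.3.6 and Appendices 7 and 8 as they are on this point.

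The cost is one sentence, carried in the next amendment. No visit or test is added, because Section 8.3.3 already contains both.

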Appendix 2. ECOG Status Scores

Status	Eastern Cooperative Oncology Group (ECOG) Performance Status**
0	Fully active, able to carry on all pre-disease performance without restriction.
1	Restricted in physically strenuous activity but ambulatory and able to carry out work of a light or sedentary nature, eg, light housework, office work.
2	Ambulatory and capable of all self-care, but unable to carry out any work activities. Up and about more than 50% of waking hours.
3	Capable of only limited self-care, confined to bed or chair more than 50% of waking hours.
4	Completely disabled. Cannot carry on any self-care. Totally confined to bed or chair.
5	Dead.

Available at: http://www.ecog.org/general/perf_stat.html. Accessed January 4, 2008.

Appendix 3. Cockcroft-Gault Formula for Estimating Creatinine Clearance

$$C_{cr} = \frac{(140 - \text{age}) \times \text{Body Weight (kg)}}{(\text{Serum creatinine mg/dL}) \times 72}$$

Note:

- Multiply by 0.85 for women
- Use with caution in cirrhosis and muscle wasting
- To convert μmol (micromoles)/L of creatinine to mg/dL, divide by 88.4.

Appendix 4. Inhibitors and Inducers of CYP3A

Inhibitors and inducers of CYP3A enzymes are defined as follows. Refer to [Section 6.1.2.1](#) on instructions for concomitant use of CYP3A inhibitors and inducers with ibrutinib. Further information can be found at the following website: <http://medicine.iupui.edu/clinpharm/ddis/main-table/>.

Inhibitors of CYP3A	Inducers of CYP3A
Strong inhibitors:	
indinavir	carbamazepine
nefnavir	efavirenz
ritonavir	nevirapine
clarithromycin	barbiturates
itraconazole	glucocorticoids
ketoconazole	modafinil
nefazodone	oxcarbazepine
saquinavir	phenobarbital
suboxone	phenytoin
telithromycin	pioglitazone
cobicistat	rifabutin
boceprevir	rifampin
mibefradil	St. John's Wort
telaprevir	troglitazone
troleandomycin	
posaconazole	
Moderate inhibitors:	
aprepitant	
amprenavir	
amiodarone	
atazanavir	
ciprofloxacin	
crizotinib	
darunavir/ritonavir	
dronedarone	
erythromycin	
diltiazem	
fluconazole	
fosamprenavir	
grapefruit juice	
Seville orange juice	
verapamil	
voriconazole	
imatinib	
Weak inhibitors:	
cimetidine	
fluvoxamine	
All other inhibitors:	
chloramphenicol	
delavirdine	
diethyl-dithiocarbamate	
gestodene	
mifepristone	
norfloxacin	
norfluoxetine	
star fruit	

Appendix 5. Revised International Working Group Response Criteria for Malignant Lymphoma (Cheson 2007) – Phase 1b Only

Response Categories				
Response	Definition	Nodal Masses	Spleen, Liver	Bone Marrow
CR	Disappearance of all evidence of disease	a) FDG-avid or PET positive prior to therapy; mass of any size permitted if PET negative b) Variably FDG-avid or PET negative; regression to normal size on CT	Not palpable, nodules disappeared	Infiltrate cleared on repeat biopsy; if indeterminate by morphology, immunohistochemistry should be negative
PR	Regression of measurable disease and no new sites	$\geq 50\%$ decrease in SPD of up to 6 largest dominant masses; no increase in size of other nodes a) FDG-avid or PET positive prior to therapy; one or more PET positive at previously involved sites b) Variably FDG-avid or PET negative; regression on CT	$\geq 50\%$ decrease in SPD of nodules (for single nodule in greatest transverse diameter); no increase in size of liver or spleen	Irrelevant if positive prior to therapy; cell type should be specific
SD	Failure to attain CR/PR or PD	a) FDG-avid or PET positive prior to therapy; PET positive at prior sites of disease and no new sites on CT or PET b) Variably FDG-avid or PET negative; no change in size of previous lesions on CT		
Relapsed disease or PD	Any new lesion or increase by $\geq 50\%$ of previously involved sites from nadir	Appearance of a new lesion(s) > 1.5 cm in any axis, $\geq 50\%$ increase in SPD of more than one node, or $\geq 50\%$ increase in longest diameter of a previously identified node > 1 cm in short axis Lesions PET positive if FDG-avid lymphoma or PET positive prior to therapy	$> 50\%$ increase from nadir in the SPD of any previous lesions	New or recurrent involvement

Abbreviations: CR, complete remission; FDG, (¹⁸F) fluorodeoxyglucose; PET, positron emission tomography; CT, computerized tomography; PR, partial remission; SPD, sum of the product of the diameters; SD, stable disease; PD, progressive disease

Appendix 6. Revised International Working Group Response Criteria for Malignant Lymphoma or Lugano Classification (Cheson 2014) – Phase 2 only

Evaluation, Staging, and Response Assessment for Non-Hodgkin Lymphoma: The Lugano Classification (according to Cheson 2014)

Evaluation, staging, and response criteria are summarized in 3 Tables below.

Table 1: Criteria for Involvement of Site

Tissue Site	Clinical	FDG Avidity	Test	Positive Finding
Lymph nodes	Palpable	FDG-avid histologies	PET-CT	Increased FDG uptake
		Non avid disease	CT	Unexplained node enlargement
Spleen	Palpable	FDG-avid histologies	PET-CT	Diffuse uptake, solitary mass, miliary lesions, nodules
		Non avid disease	CT	>13 cm in vertical length, mass, nodules
Liver	Palpable	FDG-avid histologies	PET-CT	Diffuse uptake, mass
		Non avid disease	CT	Nodules
CNS	Signs, symptoms		CT	Mass lesion(s)
			MRI	Leptomeningeal infiltration, mass lesions
			CSF assessment	Cytology, flow cytometry
Other (eg, skin, lung, GI tract, bone, bone marrow)	Site dependent		PET-CT ^a , biopsy	Lymphoma involvement

Abbreviations: CSF, cerebrospinal fluid; CT, computed tomography; FDG, fluorodeoxyglucose; MRI, magnetic resonance imaging; PET, positron emission tomography.

a: PET-CT is adequate for determination of bone marrow involvement and can be considered highly suggestive for involvement of other extralymphatic sites. Biopsy confirmation of those sites can be considered if necessary.

Table 2: Staging System for Primary Nodal Lymphomas

Stage	Involvement	Extranodal (E) Status
Limited		
I	One node or a group of adjacent nodes	Single extranodal lesions without nodal involvement
II	Two or more nodal groups on the same side of the diaphragm	Stage I or II by nodal extent with limited contiguous extranodal involvement
II bulky ^a	II as above with “bulky” disease	Not applicable
Advanced		
III	Nodes on both sides of the diaphragm; nodes above the diaphragm with spleen involvement	Not applicable
IV	Additional noncontiguous extralymphatic involvement	Not applicable

NOTE: Extent of disease is determined by positron emission tomography-computed tomography for avid lymphomas and computed tomography for nonavid histologies. Tonsils, Waldeyer's ring, and spleen are considered nodal tissue.

^a Whether stage II bulky disease is treated as limited or advanced disease may be determined by histology and a number of prognostic factors.

Table 3: Criteria for Response Assessment of Non-Hodgkin's Lymphoma

Response	Site	PET-CT-Based Response	CT-Based Response
Complete	Lymph nodes and extralymphatic sites	Complete metabolic response Score 1, 2, or 3 ^a with or without a residual mass on 5PS ² It is recognized that in Waldeyer's ring or extranodal sites with high physiologic uptake or with activation within spleen or marrow (eg, with chemotherapy or myeloid colony-stimulating factors), uptake may be greater than normal mediastinum and/or liver. In this circumstance, complete metabolic response may be inferred if uptake at sites of initial involvement is no greater than surrounding normal tissue even if the tissue has high physiologic uptake	Complete radiologic response (all of the following) Target nodes/nodal masses must regress to ≤ 1.5 cm in LD _i No extralymphatic sites of disease
	Non measured lesion	Not applicable	Absent
	Organ enlargement	Not applicable	Regress to normal
	New lesions	None	None
	Bone marrow	No evidence of FDG-avid disease in marrow	Normal by morphology; if determinate, IHC negative
Partial	Lymph nodes and extralymphatic sites	Partial metabolic response Score 4 or 5 ^b with reduced uptake compared with baseline and residual mass(es) of any size At interim, these findings suggest responding disease At end of treatment, these findings indicate residual disease	Partial remission (all of the following) $\geq 50\%$ decrease in SPD of up to 6 target measurable nodes and extranodal sites When a lesion is too small to measure on CT, assign 5 mm \times 5 mm as the default value When no longer visible, 0 \times 0 mm For a node > 5 mm \times 5 mm, but smaller than normal, use actual measurement for calculation
	Nonmeasured lesion	Not applicable	Absent/normal, regressed, but no increase
	Organ enlargement	Not applicable	Spleen must have regressed by $> 50\%$ in length beyond normal
	New lesions	None	None
	Bone marrow	Residual uptake higher than uptake in normal marrow but reduced compared with baseline (diffuse uptake compatible with reactive changes from chemotherapy allowed). If there are persistent focal changes in the marrow in the context of a nodal response, consideration should be given to further evaluation with MRI or biopsy or an interval scan	Not applicable

Response	Site	PET-CT-Based Response	CT-Based Response
No response or stable disease	Lymph nodes and extralymphatic sites	No metabolic response	Stable disease
		Score 4 or 5 with no significant change in FDG uptake from baseline at interim or end of treatment	<50% decrease from baseline in SPD of up to 6 dominant, measurable nodes and extranodal sites; no criteria for progressive disease are met
		Non measured lesion	No increase consistent with progression
		Organ enlargement	No increase consistent with progression
		New lesions	None
Progressive disease	Individual target nodes/nodal masses	No change from baseline	Not applicable
		Progressive metabolic disease Score 4 or 5 with an increase in intensity of uptake from baseline and/or New FDG-avid foci consistent with lymphoma at interim or end-of-treatment assessment	Progressive disease requires at least 1 of the following: PPD progression: An individual node/lesion must be abnormal with: LDi >1.5 cm and Increase by ≥50% from PPD nadir and An increase in LDi or SDi from nadir. 0.5 cm for lesions ≤2 cm 1.0 cm for lesions >2 cm In the setting of splenomegaly, the splenic length must increase by >50% of the extent of its prior increase beyond baseline (eg, a 15-cm spleen must increase to >16 cm). If no prior splenomegaly, must increase by at least 2 cm from baseline New or recurrent splenomegaly
	Extranodal lesions	None	New or clear progression of preexisting nonmeasured lesions
		New FDG-avid foci consistent with lymphoma rather than another etiology (eg, infection, inflammation). If uncertain regarding etiology of new lesions, biopsy or interval scan may be considered	Regrowth of previously resolved lesions A new node >1.5 cm in any axis A new extranodal site >1.0 cm in any axis; if <1.0 cm in any axis, its presence must be unequivocal and must be attributable to lymphoma Assessable disease of any size unequivocally attributable to lymphoma
		New lesions	Assessable disease of any size unequivocally attributable to lymphoma
	Bone marrow	New or recurrent FDG-avid foci	New or recurrent involvement

Abbreviations: 5PS, 5-point scale; CT, computed tomography; FDG, fluorodeoxyglucose; IHC, immunohistochemistry; LDi, longest transverse diameter of a lesion; MRI, magnetic resonance imaging; PET, positron emission tomography; PPD, cross product of the LDi and perpendicular diameter; SDi, shortest axis perpendicular to the LDi; SPD, sum of the product of the perpendicular diameters for multiple lesions.

^a A score of 3 in many subjects indicates a good prognosis with standard treatment, especially if at the time of an interim scan. However, in trials involving PET where de-escalation is investigated, it may be preferable to consider a score of 3 as inadequate response (to avoid undertreatment). Measured dominant lesions: Up to six of the largest dominant nodes, nodal masses, and extranodal lesions selected to be clearly measurable in two diameters. Nodes should preferably be from disparate regions of the body and should include, where applicable, mediastinal and retroperitoneal areas. Non-nodal lesions include those in solid organs (eg, liver, spleen, kidneys, lungs), GI involvement, cutaneous lesions, or those noted on palpation. Nonmeasured lesions: Any disease not selected as measured, dominant disease and truly assessable disease should be considered not measured. These sites include any nodes, nodal masses, and extranodal sites not selected as dominant or measurable or that do not meet the requirements for measurability but are still considered abnormal, as well as truly assessable disease, which is any site of suspected disease that would be difficult to follow quantitatively with measurement, including pleural effusions, ascites, bone lesions, leptomeningeal disease, abdominal masses, and other lesions that cannot be confirmed and followed by imaging. In Waldeyer's ring or in extranodal sites (eg, GI tract, liver, bone marrow), FDG uptake may be greater than in the mediastinum with complete metabolic response, but should be no higher than surrounding normal physiologic uptake (eg, with marrow activation as a result of chemotherapy or myeloid growth factors).

^b PET 5PS: 1, no uptake above background; 2, uptake \leq mediastinum; 3, uptake $>$ mediastinum but \leq liver; 4, uptake moderately $>$ liver; 5, uptake markedly higher than liver and/or new lesions; X, new areas of uptake unlikely to be related to lymphoma.

Appendix 7. Risks of Fetal Exposure, Pregnancy Testing Guidelines and Acceptable Birth Control Methods (for US Sites only)

Risks Associated with Pregnancy

The use of lenalidomide in pregnant females and nursing mothers has not been studied nor has the effect of the lenalidomide on human eggs and sperm. Lenalidomide is structurally related to thalidomide. Thalidomide is a known human teratogenic active substance that causes severe life-threatening birth defects. An embryofetal development study in animals indicates that lenalidomide produced malformations in the offspring of female monkeys who received the drug during pregnancy. The teratogenic effect of lenalidomide in humans cannot be ruled out. Therefore, a risk minimization plan to prevent pregnancy must be observed.

All study participants must be registered into the mandatory Revlimid REMSTM program, and be willing and able to comply with the requirements of Revlimid REMSTM. **(for US sites only)**

Criteria for females of childbearing potential (FCBP)

This protocol defines a female of childbearing potential as a sexually mature female who: 1) has not undergone a hysterectomy or bilateral oophorectomy or 2) has not been naturally postmenopausal for at least 24 consecutive months (ie, has had menses at any time in the preceding 24 consecutive months).

The Investigator must ensure that:

- Females of childbearing potential comply with the conditions for pregnancy risk minimization, including confirmation that she has an adequate level of understanding
- Females NOT of childbearing potential acknowledge that she understands the hazards and necessary precautions associated with the use of lenalidomide
- Male patients taking lenalidomide acknowledge that he understands that traces of lenalidomide have been found in semen, that he understands the potential teratogenic risk if engaged in sexual activity with a female of childbearing potential or pregnant female, and that he understands the need for the use of a condom even if he has had a vasectomy, if engaged in sexual activity with a female of childbearing potential or pregnant female.

Contraception

Females of childbearing potential (FCBP) enrolled in this protocol must agree to use two reliable forms of contraception simultaneously or to practice complete abstinence from heterosexual intercourse during the following time periods related to this study: 1) for at least 28 days before starting lenalidomide; 2) throughout the entire duration of lenalidomide treatment; 3) during dose interruptions; and 4) for at least 28 days after lenalidomide discontinuation.

